APPENDIX IV

Acute Graft Versus Host Disease Staging and Grading Table

Clinical Stage of acute GVHD according to Organ System

| Stage | Skin | Liver | Intestine |
|-------|---|---------------------|--|
| + | Maculopapular rash <25% of body surface | Bilirubin 2-3mg/dl | >500-1000 ml diarrhea per day or (nausea, anorexia or vomiting with biopsy (EGD) confirmation of upper GI GVHD |
| ++ | Maculopapular rash 25-50% of body surface | Bilirubin 3-6mg/dl | >1000-1500 ml diarrhea per day |
| +++ | Maculopapular rash >50% body surface area or Generalized erythroderma | Bilirubin 6-15mg/dl | >1500 ml diarrhea per day |
| ++++ | Generalized erythroderma with bullous formation and desquamation | Bilirubin >15mg/dl | >1500 ml diarrhea per day plus severe abdominal pain with or without ileus |

Overall Clinical Grading of Severity of acute GVHD

| Grade | Skin | Liver | GI |
|------------------|------|----------------|-----|
| I | 1-2 | 0 | 0 |
| II ^A | 0 | 0-1 | 1 |
| | 0 | 1 | 0-1 |
| | 1-3 | 0-1 | 1 |
| | 1-3 | 1 | 0-1 |
| | 3 | 0 | 0 |
| III ^A | 0-3 | 2-3 | 0-2 |
| | 0-3 | 0-3 | 2-3 |
| | 0-3 | 4 ^B | 0-3 |
| IV ^A | 0-3 | 0-4 | 4 |
| | 4 | 0-4 | 0-4 |

- A. Grade II-IV GVHD with only single organ involvement should be biopsy confirmed.
- B. If Karnofsky performance status is $\leq 30\%$, then Grade IV.

APPENDIX V

Grading of Chronic Graft Versus Host Disease

Definitions:

Progressive: Direct continuation from preceding acute GVHD.

Quiescent: Arising after complete resolution of acute GVHD.

de Novo: No preceding GVHD.

Subclinical disease: Characteristic pathology findings on both blind oral and skin biopsies in absence of clinical signs or symptoms.

Clinical disease: Multi-organ clinical manifestations and positive skin and oral biopsies

Limited cGVHD: Either or both of the following:

1. Localized skin involvement
2. Hepatic dysfunction due to cGVHD

Extensive cGVHD: Either

1. Generalized skin involvement
2. Localized skin involvement and/or hepatic dysfunction due to chronic GVHD

PLUS

3. Liver histology showing chronic aggressive hepatitis, bridging necrosis or cirrhosis, OR
4. Eye involvement with Schirmer's test with less than 5 mm wetting, OR
5. Positive lip biopsy
6. Involvement of any other target organ

Reference: Chronic Graft Versus Host Disease: Pathology, diagnosis, treatment and prognostic factors, BMT – Exp Hem Today 1988

APPENDIX VI

HD Therapy/Transplant therapy (All testing (except BM bx 4 weeks) has to be completed no more than 28 days prior to starting treatment)

| Required studies | Pre adm it | Day -17 | Day -13 | Day -12 | Day -11 | Day -10 | Day -9 | Day -8 | Day -7 | Day -6 | Day -5 | Day -4 | Day -3 | Day -2 | Day -1 | Day 0 | Day 1 | Day 2 | Day 3 | Day 4 | Day 6 | Day 7 | Day 100 | Day 180 | Yearly X 2 years | |
|---------------------------------------|------------|---------|---------|---------|---------|---------|--------|--------|--------|--------|--------|--------|--------|--------|--------|-------|-------|-------|-------|-------|-------|-------|---------|---------|------------------|---|
| CBC,Diff, PLT++* | X | X | X | X | X | X | | | | X | | | | X | | X | X | X | X | X | | | X | | X | |
| Sma- 7 | X | X | X | X | X | X | | | | X | | | | X | | X | X | X | X | X | | | X | | X | |
| SMA-12 ++ | X | X | | X | | X | | | | | | | | X | | | X | | X | | | | | X | | X |
| MG ++ | X | X | | X | | X | | | | | | | | X | | | | | X | | | | | | | |
| Hepatitis a,b,c | X | | | | | | | | | | | | | | | | | | | | | | | | | |
| HIV | X | | | | | | | | | | | | | | | | | | | | | | | | | |
| PT,PTT | X | | | | | | | | | | | | | | | | | | | | | | | | | |
| UA | X | | | | | | | | | | | | | | | | | | | | | | | | | |
| 24hr Crea cl | X | | | | | | | | | | | | | | | | | | | | | | | | | |
| Pregnancy test | X | | | | | | | | | | | | | | | | | | | | | | | | | |
| CMV,HSV/HZ V | X | | | | | | | | | | | | | | | | | | | | | | | | | |
| Immunoglobulin | X | | | | | | | | | | | | | | | | | | | | | | | | | |
| PFT | X | | | | | | | | | | | | | | | | | | | | | | | | | |
| EKG | X | | | | | | | | | | | | | | | | | | | | | | | | | |
| ++CXR | X | | | | | | | | | | | | | | | | | | | | | | | | | |
| CT Scan Chest, ABD | X | | | | | | | | | | | | | | | | | | | | | | | | | |
| ECHO or MUGA | X | | | | | | | | | | | | | | | | | | | | | | | | | |
| LP see 6.1g | X | | | | | | | | | | | | | | | | | | | | | | | | | |
| BM asp, bx, cytogenetics | X | | | | | | | | | | | | | | | | | | | | | | X | | X | |
| Dilantin level | | | X | | | | | | | | | | | | | | | | | | | | | | | |
| Busulfan levels | | | XX | | XX* | * | | | | | | | | | | | | | | | | | | | | |
| TREATMENT | | | | | | | | | | | | | | | | | | | | | | | | | | |
| Dilantin | | X | X | X | X | X | X | X | X | X | X | X | X | X | X | | | | | | | | | | | |
| Busulfan | | | X | XX** | X | X | X | X | X | | | | | | | | | | | | | | | | | |
| FTBI | | | | | | | | | | X | X | X | X | | | | | | | | | | | | | |
| VP-16 | | | | | | | | | | | | | | X | X | | | | | | | | | | | |
| PSC's or BM | | | | | | | | | | | | | | | | | | | X | | | | | | | |
| CNS Disease patients see section 6.53 | | | | | | | | | | | | | | | | | | | | | | | | | | |

\$ Dilantin will be given daily consecutively until day -14

++ Every Monday, Wednesday, Friday during hospitalization, CXR to be done weekly

XX blood sample shipment

** If required

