- e). Hepatic damage, which can occur in combination with cytoxan or as a single agent and can result in significant hepatic toxicity which, can be fatal.
- f). Temporary hyperpigmentation of the skin and nail bed changes.
- g). Grand mal seizures which can be prevented by the prophylactic administration of Dilantin.

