6.2 Preparative Chemotherapy Regimen

Rev. 8/12/02

* Patient to sign consent form before starting Dilantin.

Rev. 11/8/01

Friday/Day -18

Begin dilantin 300mg/p.o. t.i.d. times 1 day, then 300mg/p.o./IV daily times 14 days.

Tuesday/Day -14

Admission or outpatient, dilantin blood levels will be checked and dose adjusted as needed to meet therapeutic range. Further adjustments if clinically indicated. Busulfan test dose administered at 6 a.m. as a single dose. The I/V dose is calculated as follows:

1. Body surface area (BSA) is calculated by the equation:

$$\text{BSA} = \frac{(\text{Actual body wt.(kg)} \times \text{height (cm)})}{3600}$$

Rev. 6/13/02

2. 22mg/m² I/V Busulfan will be given over 2 hours. Blood levels will be obtained with the first dose as per appendix 1 and will be performed at City of Hope.

Rev. 11/8/01

Wednesday/Day -13

Busulfan AUC will be calculated by standard methods available in the City of Hope Analytical Pharmacology Core Facility (APCF). The resulting AUC will be used to determine the dose required to achieve an AUC of 800 $\mu\text{M}^* \text{min}$ according to the following formula:

$$\text{Adj dose} = \text{Current dose} \times \frac{800\mu\text{M}^* \text{ min}}{\text{test dose AUC}}$$

Rev. 6/13/02

The maximum dose given will not exceed 32mg/m². There is no limit on dose reduction Busulfan dose will only be adjusted for AUC's <700 or >900 $\mu\text{M}^* \text{min}$.

Thursday/Day -12

The adjusted dose Busulfan dose will be given at 6 a.m. and blood levels will be repeated. Further dose adjustments will be performed if AUC >1000.

Friday/Day -11

Patient admitted to BMT or receive further dose of Busulfan in clinic.

Busulfan dosing restarted at 6 p.m. and is repeated every 6 hours for a total of 14 doses.

Tuesday/Day -7

Fractionated TBI will be given at 120 cGy per fraction for a total of 4 days for a total of 10 fractions for a total dose of 1200 cGy. See Appendix II.

Saturday/Day -3

VP-16 30mg/kg based on adjusted ideal body weight will be administered.

Tuesday/Day 0

PSC reinfusion/or BM infusion

See Appendix 3 for PSC Collection

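### Section 6.2, the Appendix VI calendar and its footnote do not give one consistent course for Dilantin, the seizure prophylaxis for busulfan

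*Combined protocol and SAP*

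**What the plan says.** Section 6.2 opens the preparative regimen on day -18 with this instruction: "Begin dilantin 300mg/p.o. t.i.d. times 1 day, then 300mg/p.o./IV daily times 14 days". On day -14 it has the Dilantin blood level checked and the dose adjusted if necessary, with later adjustment left open.

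Section 6.2 dates busulfan as follows:
- Day -14: "Busulfan test dose administered at 6 a.m. as a single dose".
- Day -12: "The adjusted dose Busulfan dose will be given at 6 a.m. and blood levels will be repeated".
- Day -11: "Busulfan dosing restarted at 6 p.m. and is repeated every 6 hours for a total of 14 doses".

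Appendix VI charts the same treatment on a calendar. Its column headings go from the pre-admission column to day -17 and then straight to day -13. The Dilantin row has 14 marks. As the table reads in the public text, they fall under day -17 and then days -13 to -1. The footnote below the table says "Dilantin will be given daily consecutively until day -14".

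Section 3.15, item g, gives the purpose of the drug: "Grand mal seizures which can be prevented by the prophylactic administration of Dilantin".

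**The concern.** A study calendar is a working reference for ward and clinic staff. Here it cannot be matched to the treatment section for a prophylactic drug. The first day differs (day -18 against day -17). Two days on which Section 6.2 schedules treatment, day -18 (first Dilantin) and day -14 (busulfan test dose), have no column. The footnote names a day as the end of daily dosing that neither Section 6.2 nor the calendar row supports as an end.

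What is at stake is patient safety. The protocol relies on Dilantin to prevent busulfan seizures, and someone who took the footnote alone at face value would leave most of the busulfan course uncovered.

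**Working it through.** No sample-size or power figure is involved. The check counts days and doses.

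**1. Dilantin course in Section 6.2.** One loading day on day -18, then 14 daily doses from day -17. Last day = -17 + 13 = day -4, so 15 days in all. If the 14 days are taken to include the loading day, the last day = -18 + 13 = day -5.

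**2. Busulfan doses in Section 6.2.**
- Test dose on day -14 at 06:00: 1.
- Adjusted dose on day -12 at 06:00: 1.
- From day -11 at 18:00, 14 doses every 6 hours. The last comes 13 × 6 = 78 hours after the first, at 00:00 on day -7. By day: 1 (day -11) + 4 + 4 + 4 (days -10, -9, -8) + 1 (day -7) = 14.
- Total: 1 + 1 + 14 = 16.

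**3. Doses after each possible end of Dilantin.**

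| Reading | Last Dilantin day | Busulfan doses after it |
|---|---|---|
| Section 6.2 | day -4 (or -5) | 0 of 16 |
| Footnote as a stop, day -14 included | day -14 | 15 of 16 |
| Footnote as a stop, day -14 excluded | day -15 | 16 of 16 |
| Footnote as a bridge to the day -13 column | set by the calendar row, well past day -14 | depends on the row |

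If the 14 doses from day -11 were read as including the first two, 13 of 14 would follow day -14, and the picture would not change. The distance between the literal footnote and Section 6.2 is 14 - 4 = 10 days, or 14 - 5 = 9 days on the alternative count.

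**4. The bridge reading.** The headings leave out days -16, -15 and -14. Daily dosing through day -14 fills exactly those three days, and the row resumes at day -13. On this reading the footnote and the row form one unbroken course, and the footnote sets no stop day.

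**5. How far the calendar row can be trusted.** As extracted, its last mark is under day -1. Other rows show that the columns are not reliably aligned. The irradiation marks begin under day -6, although Section 6.2 and Appendix II start on day -7 (one column late). The infusion mark is under day 3, although it belongs on day 0 (three columns late). Moving the last Dilantin mark by one column gives day -2, and by three gives day -4. The end day cannot be read from the row, but on any of these placements it lies at least 10 days after day -14.

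**The case against.** The strongest reply is that the footnote was never a stop instruction. It fits the three missing columns exactly, and the Dilantin row has 13 further marks from day -13 onward. Section 6.2 also checks the level and adjusts the dose on day -14, which makes little sense if the drug ends that day. In addition, the footnote's marker ($) appears nowhere in the extracted table, so its anchor cannot be seen. Staff would have to ignore both the row above the footnote and the treatment section in order to stop on day -14.

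Most of this stands. A reader might infer that the protocol, through its calendar, ends prophylaxis before 15 of the 16 busulfan doses. The documents do not support that as the footnote's only meaning, or even its likeliest one. The 15 of 16 is the consequence of one literal reading.

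A reader might also infer that seizures caused by early stopping would count toward the stopping rule in Section 12.3, since neurotoxicity is among its examples. That section refers to severe treatment-related complications and ties its examples to day 100 after transplant. It does not say whether a seizure during pre-transplant busulfan qualifies. The link is conjecture, and the point does not rest on it.

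The reply does not remove the mismatch. The footnote does not say that it is a bridge, and the different first day and the absent day -18 and day -14 columns remain even if it is one.

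**Conclusion.** The Dilantin course is stated inconsistently, and the inconsistency survives every reading of the footnote. Section 6.2 gives days -18 to about -4. The calendar starts at day -17 and runs well past day -14 to an end day that cannot be fixed from the extracted table. The footnote, read literally, names an end day 9 to 10 days before that of Section 6.2. The Section 6.2 course covers all 16 busulfan doses, while the literal footnote leaves 15 of 16 uncovered.

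This rests on two assumptions: that the column headings are complete as extracted, and that the 14 doses are those from day -11 onward. The first affects only the missing-column part of the finding and the bridge reading. The second does not change the conclusion. The defect is one of wording and layout in operational text, with no effect on sample size or the planned estimates. It merits correction because it concerns a safety measure and costs almost nothing to put right.

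**What to change.** Reconcile Section 6.2, the calendar's Dilantin row, its column headings and the footnote, so that one start day and one stop day for Dilantin appear in all of them. Give the calendar a column for every day on which Section 6.2 schedules treatment, including days -18 and -14, or state clearly which days are not charted. Reword the footnote to say whether it covers only the uncharted days or marks the end of the course, and show which row or cell it belongs to. Check the other treatment rows against Section 6.2 at the same time.

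Which course applies is for the clinical team to decide. The cost is a correction to the calendar and footnote, and to Section 6.2 if the team finds that it needs one.

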APPENDIX VII

CTC Version 2.0
Publish Date: April 30, 1999

COMMON TOXICITY CRITERIA (CTC)

| Adverse Event | Grade | | | | |
|---|--------|---|--|---|--|
| | 0 | 1 | 2 | 3 | 4 |
| ALLERGY/IMMUNOLOGY | | | | | |
| Allergic reaction/ hypersensitivity (including drug fever) | none | transient rash, drug fever: <38°C (<100.4°F) | urticaria, drug fever ≥38°C (≥100.4°F), and/or asymptomatic bronchospasm | symptomatic bronchospasm, requiring parenteral medication(s), with or without urticaria; allergy-related edema/angioedema | anaphylaxis |
| Note: Isolated urticaria, in the absence of other manifestations of an allergic or hypersensitivity reaction, is graded in the DERMATOLOGY/SKIN category. | | | | | |
| Allergic rhinitis (including sneezing, nasal stuffiness, postnasal drip) | none | mild, not requiring treatment | moderate, requiring treatment | - | - |
| Autoimmune reaction | none | serologic or other evidence of autoimmune reaction but patient is asymptomatic (e.g., vitiligo), all organ function is normal and no treatment is required | evidence of autoimmune reaction involving a non- essential organ or function (e.g., hypothyroidism), requiring treatment other than immunosuppressive drugs | reversible autoimmune reaction involving function of a major organ or other adverse event (e.g., transient colitis or anemia), requiring short-term immunosuppressive treatment | autoimmune reaction causing major grade 4 organ dysfunction; progressive and irreversible reaction; long-term administration of high- dose immuno- suppressive therapy required |
| Also consider Hypothyroidism, Colitis, Hemoglobin, Hemolysis. | | | | | |
| Serum sickness | none | - | - | present | - |
| Urticaria is graded in the DERMATOLOGY/SKIN category if it occurs as an isolated symptom. If it occurs with other manifestations of allergic or hypersensitivity reaction, grade as Allergic reaction/hypersensitivity above. | | | | | |
| Vasculitis | none | mild, not requiring treatment | symptomatic, requiring medication | requiring steroids | ischemic changes or requiring amputation |
| Allergy/Immunology - Other (Specify, _____) | none | mild | moderate | severe | life-threatening or disabling |
| AUDITORY/HEARING | | | | | |
| Conductive hearing loss is graded as Middle ear/hearing in the AUDITORY/HEARING category. | | | | | |
| Earache is graded in the PAIN category. | | | | | |
| External auditory canal | normal | external otitis with erythema or dry desquamation | external otitis with moist desquamation | external otitis with discharge, mastoiditis | necrosis of the canal soft tissue or bone |
| Note: Changes associated with radiation to external ear (pinnae) are graded under Radiation dermatitis in the DERMATOLOGY/SKIN category. | | | | | |

| Adverse Event | Grade | | | | |
|---|------------------------------|--|---|--|--|
| | 0 | 1 | 2 | 3 | 4 |
| Inner ear/hearing | normal | hearing loss on audiology only | tinnitus or hearing loss, not requiring hearing aid or treatment | tinnitus or hearing loss, correctable with hearing aid or treatment | severe unilateral or bilateral hearing loss (deafness), not correctable |
| Middle ear/hearing | normal | serous otitis without subjective decrease in hearing | serous otitis or infection requiring medical intervention; subjective decrease in hearing; rupture of tympanic membrane with discharge | otitis with discharge, mastoiditis or conductive hearing loss | necrosis of the canal soft tissue or bone |
| Auditory/Hearing - Other (Specify: _____) | normal | mild | moderate | severe | life-threatening or disabling |
| BLOOD/BONE MARROW | | | | | |
| Bone marrow cellularity | normal for age | mildly hypocellular or $\leq 5\%$ reduction from normal cellularity for age | moderately hypocellular or $>25 - \leq 50\%$ reduction from normal cellularity for age or >2 but <4 weeks to recovery of normal bone marrow cellularity | severely hypocellular or $>50 - \leq 75\%$ reduction in cellularity for age or 4 - 6 weeks to recovery of normal bone marrow cellularity | aplasia or >6 weeks to recovery of normal bone marrow cellularity |
| Normal ranges: | | | | | |
| children (≤18 years) | 90% cellularity average | | | | |
| younger adults (19-59) | 60 - 70% cellularity average | | | | |
| older adults (≥60 years) | 50% cellularity average | | | | |
| Note: Grade Bone marrow cellularity only for changes related to treatment not disease. | | | | | |
| CD4 count | WNL | $<LLN - 500/\text{mm}^3$ | $200 - <500/\text{mm}^3$ | $50 - <200/\text{mm}^3$ | $<50/\text{mm}^3$ |
| Haptoglobin | normal | decreased | - | absent | - |
| Hemoglobin (Hgb) | WNL | $<LLN - 10.0 \text{ g/dL}$ $<LLN - 100 \text{ g/L}$ $<LLN - 6.2 \text{ mmol/L}$ | $8.0 - <10.0 \text{ g/dL}$ $80 - <100 \text{ g/L}$ $4.9 - <6.2 \text{ mmol/L}$ | $6.5 - <8.0 \text{ g/dL}$ $65 - <80 \text{ g/L}$ $4.0 - <4.9 \text{ mmol/L}$ | $<6.5 \text{ g/dL}$ $<65 \text{ g/L}$ $<4.0 \text{ mmol/L}$ |
| For leukemia studies or bone marrow infiltration, use myelophthisic processes, if specified in the protocol | WNL | $10 - <5\%$ decrease from pretreatment | $25 - <50\%$ decrease from pretreatment | $50 - <75\%$ decrease from pretreatment | $>75\%$ decrease from pretreatment |
| Hemolysis (e.g., immune hemolytic anemia, drug-related hemolysis, other) | none | only laboratory evidence of hemolysis (e.g., direct antiglobulin test (DAT, Coombs') schistocytes) | evidence of red cell destruction and $\geq 2\text{gm}$ decrease in hemoglobin, no transfusion | requiring transfusion and/or medical intervention (e.g., steroids) | catastrophic consequences of hemolysis (e.g., renal failure, hypotension, bronchospasm, emergency splenectomy) |
| Also consider Haptoglobin, Hemoglobin. | | | | | |

| Adverse Event | 0 | 1 | 2 | 3 | 4 |
|---|------|---|---|---|---|
| Leukocytes (total WBC) | WNL | $\leq LLN - 3.0 \times 10^9/L$ $\leq LLN - 3000/mm^3$ | $\geq 2.0 - <3.0 \times 10^9/L$ $\geq 2000 - <3000/mm^3$ | $\geq 1.0 - <2.0 \times 10^9/L$ $\geq 1000 - <2000/mm^3$ | $<1.0 \times 10^9/L$ $<1000/mm^3$ |
| For BMT studies, if specified in the protocol | WNL | $\geq 2.0 - <3.0 \times 10^9/L$ $\geq 2000 - <3000/mm^3$ | $\geq 1.0 - <2.0 \times 10^9/L$ $\geq 1000 - <2000/mm^3$ | $\geq 0.5 - <1.0 \times 10^9/L$ $\geq 500 - <1000/mm^3$ | $<0.5 \times 10^9/L$ $<500/mm^3$ |
| For pediatric BMT studies (using age, race and sex normal values), if specified in the protocol | | $27.5 - <100\% LLN$ | $25.0 - <75\% LLN$ | $22.5 - <50\% LLN$ | $<25\% LLN$ |
| Lymphopenia | WNL | $\leq LLN - 1.0 \times 10^9/L$ $\leq LLN - 1000/mm^3$ | $\geq 0.5 - <1.0 \times 10^9/L$ $\geq 500 - <1000/mm^3$ | $<0.5 \times 10^9/L$ $<500/mm^3$ | - |
| For pediatric BMT studies (using age, race and sex normal values), if specified in the protocol | | $27.5 - <100\% LLN$ | $25.0 - <75\% LLN$ | $22.5 - <50\% LLN$ | $<25\% LLN$ |
| Neutrophils/granulocytes (ANC/AGC) | WNL | $\geq 1.5 - <2.0 \times 10^9/L$ $\geq 1500 - <2000/mm^3$ | $\geq 1.0 - <1.5 \times 10^9/L$ $\geq 1000 - <1500/mm^3$ | $\geq 0.5 - <1.0 \times 10^9/L$ $\geq 500 - <1000/mm^3$ | $<0.5 \times 10^9/L$ $<500/mm^3$ |
| For BMT studies, if specified in the protocol | WNL | $\geq 1.0 - <1.5 \times 10^9/L$ $\geq 1000 - <1500/mm^3$ | $\geq 0.5 - <1.0 \times 10^9/L$ $\geq 500 - <1000/mm^3$ | $\geq 0.1 - <0.5 \times 10^9/L$ $\geq 100 - <500/mm^3$ | $<0.1 \times 10^9/L$ $<100/mm^3$ |
| For leukemia studies or bone marrow infiltrative myeloproliferative process, if specified in the protocol | WNL | $10 - <25\% \text{ decrease from baseline}$ | $25 - <50\% \text{ decrease from baseline}$ | $50 - <75\% \text{ decrease from baseline}$ | $>75\% \text{ decrease from baseline}$ |
| Platelets | WNL | $\leq LLN - 75.0 \times 10^9/L$ $\leq LLN - 75,000/mm^3$ | $\geq 50.0 - <75.0 \times 10^9/L$ $\geq 50,000 - <75,000/mm^3$ | $\geq 10.0 - <50.0 \times 10^9/L$ $\geq 10,000 - <50,000/mm^3$ | $<10.0 \times 10^9/L$ $<10,000/mm^3$ |
| For BMT studies, if specified in the protocol | WNL | $\geq 50.0 - <75.0 \times 10^9/L$ $\geq 50,000 - <75,000/mm^3$ | $\geq 20.0 - <50.0 \times 10^9/L$ $\geq 20,000 - <50,000/mm^3$ | $\geq 10.0 - <20.0 \times 10^9/L$ $\geq 10,000 - <20,000/mm^3$ | $<10.0 \times 10^9/L$ $<10,000/mm^3$ |
| For leukemia studies or bone marrow infiltrative myeloproliferative process, if specified in the protocol | WNL | $10 - <25\% \text{ decrease from baseline}$ | $25 - <50\% \text{ decrease from baseline}$ | $50 - <75\% \text{ decrease from baseline}$ | $>75\% \text{ decrease from baseline}$ |
| Transfusion: Platelets | none | - | - | yes | platelet transfusions and other measures required to improve platelet increment; platelet transfusion refractoriness associated with life-threatening bleeding (e.g., HLA or cross matched platelet transfusions) |
| For BMT studies, if specified in the protocol | none | 1 platelet transfusion in 24 hours | 2 platelet transfusions in 24 hours | 23 platelet transfusions in 24 hours | platelet transfusions and other measures required to improve platelet increment; platelet transfusion refractoriness associated with life-threatening bleeding (e.g., HLA or cross matched platelet transfusions) |
| Also consider Platelets. | | | | | |

| Adverse Event | Grade | | | | |
|---|-------------------------------------|--|--|--|--|
| | 0 | 1 | 2 | 3 | 4 |
| Transfusion: pRBCs | none | - | - | yes | - |
| ^{Pre-EMT evidence of hemolysis associated with transfusion of pRBCs as specified in the protocol} | ^{<2 u pRBC in 24 hours} | ^{>2 u pRBC in 24 hours} | ^{>24 u pRBC in 24 hours} | ^{hemolysis associated with life-threatening anemia} | ^{hemolysis associated with life-threatening anemia} |
| ^{Post-EMT evidence of hemolysis associated with transfusion of pRBCs as specified in the protocol} | ^{<15mL/kg in 24 hours} | ^{>15-50mL/kg in 24 hours} | ^{>50mL/kg in 24 hours} | ^{hemolysis associated with life-threatening anemia} | ^{hemolysis associated with life-threatening anemia} |
| ^{Also consider Hemoglobin} | | | | | |
| Blood/Bone Marrow - Other (Specify _____) | none | mild | moderate | severe | life-threatening or disabling |
| CARDIOVASCULAR (ARRHYTHMIA) | | | | | |
| Conduction abnormality/ Atrioventricular heart block | none | asymptomatic, not requiring treatment (e.g., Mobitz type I second-degree AV block, Wenckebach) | symptomatic, but not requiring treatment | symptomatic and requiring treatment (e.g., Mobitz type II second-degree AV block, third-degree AV block) | life-threatening (e.g., arrhythmia associated with CHF, hypotension, syncope, shock) |
| Nodal/junctional arrhythmia/dysrhythmia | none | asymptomatic, not requiring treatment | symptomatic, but not requiring treatment | symptomatic and requiring treatment | life-threatening (e.g., arrhythmia associated with CHF, hypotension, syncope, shock) |
| Palpitations | none | present | - | - | - |
| Note: Grade palpitations only in the absence of a documented arrhythmia. | | | | | |
| Prolonged QTc interval (QTc >0.48 seconds) | none | asymptomatic, not requiring treatment | symptomatic, but not requiring treatment | symptomatic and requiring treatment | life-threatening (e.g., arrhythmia associated with CHF, hypotension, syncope, shock) |
| Sinus bradycardia | none | asymptomatic, not requiring treatment | symptomatic, but not requiring treatment | symptomatic and requiring treatment | life-threatening (e.g., arrhythmia associated with CHF, hypotension, syncope, shock) |
| Sinus tachycardia | none | asymptomatic, not requiring treatment | symptomatic, but not requiring treatment | symptomatic and requiring treatment of underlying cause | - |
| Supraventricular arrhythmias (SVT/atrial fibrillation/flutter) | none | asymptomatic, not requiring treatment | symptomatic, but not requiring treatment | symptomatic and requiring treatment | life-threatening (e.g., arrhythmia associated with CHF, hypotension, syncope, shock) |
| Syncope (fainting) is graded in the NEUROLOGY category. | | | | | |
| Vasovagal episode | none | - | present without loss of consciousness | present with loss of consciousness | - |

| Adverse Event | Grade | | | | |
|--|--------|--|--|---|--|
| | 0 | 1 | 2 | 3 | 4 |
| Ventricular arrhythmia (PVCs/bigeminy/trigeminy/ventricular tachycardia) | none | asymptomatic, not requiring treatment | symptomatic, but not requiring treatment | symptomatic and requiring treatment | life-threatening (e.g., arrhythmia associated with CHF, hypotension, syncope, shock) |
| Cardiovascular/Arrhythmia - Other (Specify, _____) | none | asymptomatic, not requiring treatment | symptomatic, but not requiring treatment | symptomatic and requiring treatment of underlying cause | life-threatening (e.g., arrhythmia associated with CHF, hypotension, syncope, shock) |
| CARDIOVASCULAR (GENERAL) | | | | | |
| Acute vascular leak syndrome | absent | - | symptomatic, but not requiring fluid support | respiratory compromise or requiring fluids | life-threatening; requiring pressor support and/or ventilatory support |
| Cardiac-ischemia/infarction | none | non-specific T - wave flattening or changes | asymptomatic, ST - and T - wave changes suggesting ischemia | angina without evidence of infarction | acute myocardial infarction |
| Cardiac left ventricular function | normal | asymptomatic decline of resting ejection fraction of $\geq 10\%$ but $< 20\%$ of baseline value; shortening fraction $\geq 4\%$ but $< 10\%$ | asymptomatic but resting ejection fraction below LLN for laboratory or decline of resting ejection fraction $\geq 20\%$ of baseline value; $< 4\%$ shortening fraction | CHF responsive to treatment | severe or refractory CHF or requiring intubation |
| CNS cerebrovascular ischemia is graded in the NEUROLOGY category. | | | | | |
| Cardiac troponin I (cTnI) | normal | - | - | levels consistent with unstable angina as defined by the manufacturer | levels consistent with myocardial infarction as defined by the manufacturer |
| Cardiac troponin T (cTnT) | normal | $\geq 0.03 - < 0.05 \text{ ng/mL}$ | $\geq 0.05 - < 0.1 \text{ ng/mL}$ | $\geq 0.1 - < 0.2 \text{ ng/mL}$ | $\geq 0.2 \text{ ng/mL}$ |
| Edema | none | asymptomatic, not requiring therapy | symptomatic, requiring therapy | symptomatic edema limiting function and unresponsive to therapy or requiring drug discontinuation | anasarca (severe generalized edema) |
| Hypertension | none | asymptomatic, transient increase by $> 20 \text{ mmHg}$ (diastolic) or to $> 150/100^*$ if previously WNL; not requiring treatment | recurrent or persistent or symptomatic increase by $> 20 \text{ mmHg}$ (diastolic) or to $> 150/100^*$ if previously WNL; not requiring treatment | requiring therapy or more intensive therapy than previously | hypertensive crisis |

*Note: For pediatric patients, use age and sex appropriate normal values $> 95^{\text{th}}$ percentile ULV.

| Adverse Event | Grade | | | | |
|---|-------|--|---|---|---|
| | 0 | 1 | 2 | 3 | 4 |
| Hypotension | none | transient, but not requiring therapy (including transient orthostatic hypotension) | requiring brief fluid replacement or other therapy but not hospitalization; no physiologic consequences | requiring therapy and sustained medical attention, but resolves without persistent physiologic consequences | shock (associated with acidemia and impairing vital organ function due to tissue hypoperfusion) |
| Also consider: Syncope (fainting). | | | | | |
| Notes: Angina or MI is graded as Cardiac-ischemia/infarction in the CARDIOVASCULAR (GENERAL) category. | | | | | |
| For pediatric patients, systolic BP 65 mmHg or less in infants up to 1 year old and 70 mmHg or less in children older than 1 year of age, use two successive or three measurements in 24 hours. | | | | | |
| Myocarditis | none | | | CHF responsive to treatment | severe or refractory CHF |
| Operative injury of vein/artery | none | primary suture repair for injury, but not requiring transfusion | primary suture repair for injury, requiring transfusion | vascular occlusion requiring surgery or bypass for injury | myocardial infarction; resection of organ (e.g., bowel, limb) |
| Pericardial effusion/ pericarditis | none | asymptomatic effusion, not requiring treatment | pericarditis (rub, ECG changes, and/or chest pain) | with physiologic consequences | tamponade (drainage or pericardial window required) |
| Peripheral arterial ischemia | none | | brief episode of ischemia managed non-surgically and without permanent deficit | requiring surgical intervention | life-threatening or with permanent functional deficit (e.g., amputation) |
| Phlebitis (superficial) | none | | present | | |
| Notes: Injection site reaction is graded in the DERMATOLOGY/SKIN category. | | | | | |
| Thrombosis/embolism is graded in the CARDIOVASCULAR (GENERAL) category. | | | | | |
| Syncope (fainting) is graded in the NEUROLOGY category. | | | | | |
| Thrombosis/embolism | none | | deep vein thrombosis, not requiring anticoagulant | deep vein thrombosis, requiring anticoagulant therapy | embolic event including pulmonary embolism |
| Vein/artery operative injury is graded as Operative injury of vein/artery in the CARDIOVASCULAR (GENERAL) category. | | | | | |
| Visceral arterial ischemia (non-myocardial) | none | | brief episode of ischemia managed non-surgically and without permanent deficit | requiring surgical intervention | life-threatening or with permanent functional deficit (e.g., resection of ileum) |
| Cardiovascular/ General - Other (Specify) | none | mild | moderate | severe | life-threatening or disabling |

| Adverse Event | Grade | | | | |
|--|--|---|---|--|---|
| | 0 | 1 | 2 | 3 | 4 |
| COAGULATION | | | | | |
| Note: See the HEMORRHAGE category for grading the severity of bleeding events. | | | | | |
| DIC (disseminated intravascular coagulation) | absent | | | laboratory findings present with no bleeding | laboratory findings and bleeding |
| Also consider Platelets. | | | | | |
| Note: Must have increased fibrin split products or D-dimer in order to grade as DIC. | | | | | |
| Fibrinogen | WNL | 20.75 - <1.0 x LLN | 20.5 - <0.75 x LLN | 20.25 - <0.5 x LLN | <0.25 x LLN |
| For leukemia studies or bone marrow infiltrative myeloproliferative process, if specified in the protocol | WNL | <20% decrease from pre-treatment value or LLN | <20 - <40% decrease from pre-treatment value or LLN | <20 - <10% decrease from pre-treatment value or LLN | <10% decrease from pre-treatment value or LLN |
| Partial thromboplastin time (PTT) | WNL | >ULN - ≤1.5 x ULN | >1.5 - ≤ x ULN | >2 x ULN | - |
| Phlebitis is graded in the CARDIOVASCULAR (GENERAL) category. | | | | | |
| Prothrombin time (PT) | WNL | >ULN - ≤1.5 x ULN | >1.5 - ≤ x ULN | >2 x ULN | - |
| Thrombosis/embolism is graded in the CARDIOVASCULAR (GENERAL) category. | | | | | |
| Thrombotic microangiopathy (e.g., thrombotic thrombocytopenic purpura/TTP or hemolytic uremic syndrome/HUS) | absent | | | laboratory findings present without clinical consequences | laboratory findings and clinical consequences, (e.g., CNS hemorrhage/bleeding or thrombosis/embolism or renal failure) requiring therapeutic intervention |
| For BMT studies, if specified in the protocol | evidence of RBC destruction (schistocytes) without clinical consequences | evidence of RBC destruction with elevated creatinine (>1.5 x ULN) | evidence of RBC destruction with creatinine (>3 x ULN) not requiring dialysis | evidence of RBC destruction with creatinine (>3 x ULN) requiring dialysis | evidence of RBC destruction with renal failure requiring dialysis and/or encephalopathy |
| Also consider Hemoglobin, Platelets, Creatinine. | | | | | |
| Note: Must have microangiopathic changes on blood smear (e.g., schistocytes, \square met cells, red cell fragments). | | | | | |
| Coagulation - Other (Specify, _____) | none | mild | moderate | severe | life-threatening or disabling |
| CONSTITUTIONAL SYMPTOMS | | | | | |
| Fatigue (lethargy, malaise, asthenia) | none | increased fatigue over baseline, but not altering normal activities | moderate (e.g., decrease in performance status by 1 ECOG level or 20% Karnofsky or Lansky) or causing difficulty performing some activities | severe (e.g., decrease in performance status by ≥2 ECOG levels or 40% Karnofsky or Lansky) or loss of ability to perform some activities | bedridden or disabling |
| Note: See Appendix III for performance status scales. | | | | | |

| Adverse Event | Grade | | | | |
|---|--------|--|--|--|--|
| | 0 | 1 | 2 | 3 | 4 |
| Fever (in the absence of neutropenia, where neutropenia is defined as $AGC < 1.0 \times 10^9/L$) | none | 38.0 - 39.0°C (100.4 - 102.2°F) | 39.1 - 40.0°C (102.3 - 104.0°F) | $>40.0°C (>104.0°F)$ for <4 hrs | $>40.0°C (>104.0°F)$ for >24 hrs |
| Also consider Allergic reaction/hyperseasitivitry. | | | | | |
| Note: The temperature measurements listed above are oral or tympanic. | | | | | |
| Hot flashes/flushes are graded in the ENDOCRINE category. | | | | | |
| Rigors, chills | none | mild, requiring symptomatic treatment (e.g., blanket) or non-narcotic medication | severe and/or prolonged, requiring narcotic medication | not responsive to narcotic medication | - |
| Sweating (diaphoresis) | normal | mild and occasional | frequent or drenching | - | - |
| Weight gain | $<5\%$ | $5 - <10\%$ | $10 - <20\%$ | $\geq 20\%$ | - |
| Also consider Ascites, Edema, Pleural effusion (non-malignant). | | | | | |
| Weight gain associated with Veno-Occlusive Disease (VOD) for BMT studies, if specified in the protocol | $<2\%$ | $2\% - <5\%$ | $\geq 5\% - <10\%$ | $\geq 10\% \text{ or as ascites}$ | $\geq 10\% \text{ or fluid retention, including in pulmonary failure}$ |
| Also consider Ascites, Edema, Pleural effusion (non-malignant). | | | | | |
| Weight loss | $<5\%$ | $5 - <10\%$ | $10 - <20\%$ | $\geq 20\%$ | - |
| Also consider Vomiting, Dehydration, Diarrhea. | | | | | |
| Constitutional Symptoms - Other (Specify, _____) | none | mild | moderate | severe | life-threatening or disabling |
| DERMATOLOGY/SKIN | | | | | |
| Alopecia | normal | mild hair loss | pronounced hair loss | - | - |
| Bruising (in absence of grade 3 or 4 thrombocytopenia) | none | localized or in dependent area | generalized | - | - |
| Note: Bruising resulting from grade 3 or 4 thrombocytopenia is graded as Petechiae/purpura and Hemorrhage/bleeding with grade 3 or 4 thrombocytopenia in the HEMORRHAGE category, not in the DERMATOLOGY/SKIN category. | | | | | |
| Dry skin | normal | controlled with emollients | not controlled with emollients | - | - |
| Erythema multiforme (e.g., Stevens-Johnson syndrome, toxic epidermal necrolysis) | absent | - | scattered, but not generalized eruption | severe or requiring IV fluids (e.g., generalized rash or painful stomatitis) | life-threatening (e.g., exfoliative or ulcerating dermatitis or requiring enteral or parenteral nutritional support) |
| Flushing | absent | present | - | - | - |
| Hand-foot skin reaction | none | skin changes or dermatitis without pain (e.g., erythema, peeling) | skin changes with pain, not interfering with function | skin changes with pain, interfering with function | - |
| Injection site reaction | none | pain or itching or erythema | pain or swelling, with inflammation or edema | ulceration or necrosis that is severe or prolonged, or requiring surgery | - |

| Adverse Event | Grade | | | | |
|---|--------|---|--|---|---|
| | 0 | 1 | 2 | 3 | 4 |
| Nail changes | normal | discoloration or ridging (koilonychia) or pitting | partial or complete loss of nail(s) or pain in nailbeds | - | - |
| Petechiae is graded in the HEMORRHAGE category. | | | | | |
| Phosorescency | none | painless erythema | painful erythema | erythema with desquamation | - |
